Study duration	
Individual study period: approximately 3 weeks.
 
Screening should occur up to 1 week (+2 days of accepted timeframe window) prior to the Start of Treatment (Day 1). Febuxostat treatment will start 2 days before chemotherapy and continue for 7-9 days (Day 7 to Day 9). A follow-up visit will occur at Day 14 (± 2 days of accepted timeframe window).

Inclusion criteria	
Patients meeting ALL the following criteria will be eligible to enter the study:
 
 ■ male and female children of 6 to less than 12 years of age, adolescents of 12 to less than 18 years of age, and adults: 
 a. scheduled for first cytotoxic chemotherapy cycle, regardless of the line of treatment, because of

	
hematologic malignancies, and
 
b. at intermediate or high risk for TLS, andc. with serum uric acid (sUA) levels < 10 mg/dL at Visit 1 (Day 1), andd. with no access to rasburicase; 

 

 

--	--

Exclusion criteria	
Patients will not be eligible to participate in the study if they meet ANY of the following exclusion criteria:
 
1. patients known to be hypersensitive to febuxostat or to any components of the formulation; 

 
6. patients with severe renal insufficiency;7. patients with severe hepatic insufficiency;8. patients with diagnosis of Laboratory TLS (LTLS) or Clinical TLS (CTLS) at Visit 1 (Day 1). 

 

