8.3.1 Inclusion criteria

male and female children of 6 to less than 12 years of age, adolescents of 12 to less than 18 years of age and adults from 18 years:

- a. scheduled for first cytotoxic chemotherapy cycle, regardless of the line of treatment, because of hematologic malignancies, and
- b. at intermediate or high risk of TLS [4], and
- c. with serum uric acid (sUA) levels < 10 mg/dL at Visit 1 (Day 1), and
- d. with no access to rasburicase;

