9.3.4 Secondary analysis

- ***Pharmacodynamic endpoint:***

Area under plasma uric acid concentration curves (AUC sUA_{1-8}) from baseline (Visit 1, Day 1) to the Evaluation Visit (Visit 8, Day 8) will be computed for dose and age group using a trapezoidal rule which approximates the integral or the area under a curve.

A graphic example is provided in order to show which is the area considered to calculate AUC.

Figure 1

The trapezoidal rule is a numerical method to be used to approximate the integral or the area under a curve. Trapezoidal rule first involves dividing the area into a number of strips of equal width, with low limit identified with a and upper limit with b. Then, approximating the area of each strip by the area of the trapezium formed and summing these approximations, the final numerical result will be the area under the curve.

The trapezoidal rule will be presented by mean of a definite integral:

$$\int_a^b f(x)dx$$

Last observation carried forward method (LOCF) will be applied for patients who discontinued the study prematurely and a linear interpolation method will be used to impute the missing data between visits.

The pharmacodynamic analysis will be run on PK population and for exploratory reasons on ITT population.

- ***PK/PD endpoint:***

Observed exposure-response data will be descriptively and graphically summarized by age and dose group.

The aim of this analysis is to support the assumption of a comparable PK/PD relationship between pediatric patients ($\geq 6 < 18$ years of age) and adults and to evaluate if potential deviations in PK are clinically relevant.

This analysis will be conducted on the PK population.

- ***Clinical endpoints: Incidence of LTLS and CTLS***

- The assessment for LTLS from Start of Chemotherapy (Visit 3, Day 3) to the Evaluation Visit (Visit 8, Day 8) will be defined as:

1: PRESENCE 2 or more laboratory abnormalities including: a 25% increase or levels above normal for serum uric acid, potassium, and phosphate or a 25% decrease or levels below normal for calcium.

0: ABSENCE less than 2 laboratory abnormalities including: a 25% increase or levels above normal for serum uric acid, potassium, and phosphate or a 25% decrease or levels below normal for calcium.

- The assessment for CTLS from Start of Chemotherapy (Visit 3, Day 3) to the Evaluation Visit (Visit 8, Day 8) is defined as:

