13. APPENDIX

13.1 APPENDIX I: DEFINITION OF LTLS AND CTLS

Diagnosis of LTLS: LTLS is diagnosed if levels of 2 or more serum values of uric acid, potassium, phosphate or calcium are more than or less than normal at presentation or if they change by at least 25% from baseline.

ELEMENT	VALUE	CHANGE FROM BASELINE
Uric Acid	≥ 476 μmol/L (or 8 mg/dL)	25% increase
Potassium	≥ 6.0 mmol/L	25% increase
Phosphorus	≥ 1.45 mmol/L (adults) or ≥ 2.1mmol/L (children)	25% increase
Calcium	≤ 1.75 mmol/L	25% decrease

For adolescents and adults, the values of phosphorus will be considered the same for the diagnosis of LTLS.

Diagnosis of CTLS: CTLS is present when LTLS is accompanied by at least one of the following significant clinical complication: increased creatinine level ≥ 1.5 ULN, cardiac arrhythmia/sudden death or seizure. Diagnostic pathway is quite the same between adults and children, with a clarification about the creatinine ULN (if not specified by the Local Laboratory, the value has to be age/gender adjusted according to the following: > 1 <12 years, both male and female, 61.6 μmol/L; ≥ 12 < 16 years, both male and female, 88 μmol/L; ≥ 16 years, female, 105.6 μmol/L; ≥ 16 years, male, 114.4 μmol/L).

	Grade 0	Grade 1	Grade 2	Grade 3	Grade 4	Grade 5
LTLS	-	+	+	+	+	+
Creatinine	≤1.5 x ULN	1.5 x ULN	>1.5-3.0 x ULN	>3.0-6.0 x ULN	>6.0 x ULN	death
Arrhythmia	none	Intervention not indicated	Non urgent medical intervention indicated	Symptomatic and incompletely controlled medically or controlled with device	Life-threatening	death
Seizure	none	-	1 brief, generalized seizure; seizure(s) well controlled by anti convulsants or infrequent focal motor seizures not interfering with activities of daily living	Seizure in which consciousness is altered; poorly controlled seizure disorder; with breakthrough generalized seizure despite medical intervention	Seizure of any kind which are prolonged, repetitive or difficult to control	death

The CTLS grading classification (Cairo and Bishop, 2004)

13.2 APPENDIX II: EU SMPCs FOR ADENURIC® EU SMPCs FOR ADENURIC® 80 MG FILM-COATED TABLETS

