13.3 APPENDIX III: TLS RISK ASSESSMENT

PANEL A. MEDICAL DECISION TREE FOR LYMPHOMA

Important Note

- Aggressive lymphoma according to 2008 WHO classification with Bulky disease (defined as one lymphnode/tumor > 10 cm in diameter) have to be considered IRD regardless of the LDH levels;
- Follicular large cell lymphoma (grade 3b) has to be considered as aggressive lymphoma according to 2008 WHO classification;
- Patients with LRD are intermediate-risk for TLS when renal dysfunction and/or renal involvement is present;
- Patients with IRD are high-risk for TLS when renal dysfunction and/or renal involvement is present OR when uric acid, phosphate and/or potassium levels are > ULN.

Legend. HL= Hodgkin lymphoma, FL= Follicular Lymphoma, MALT= Mucosa-Associated Lymphoid Tissue, MCL= Mantel Cell Lymphoma, BL= Burkitt Lymphoma/Leukaemia, LL= Lymphoblastic Lymphoma, ALCL= Anaplastic Large Cell Lymphoma, ATL= Adult T-cell Lymphoma, DLBCL= Diffuse Large B-Cell Lymphoma, PTCL= Peripheral T-cell Lymphoma, LDH= lactate dehydrogenase, ULN= Upper Limit of Normal, WNL= Within Normal Limit, LRD= Low Risk Disease, IRD= Intermediate Risk Disease, HRD= High Risk Disease.

PANEL B. MEDICAL DECISION TREE FOR LEUKEMIA

[figure not shown]

Figure adapted from Cairo M, Coiffier B, Reiter A and Younes A on behalf of the TLS Expert Panel. *British Journal of Haematology* 2010 [4].

Important Note

- Patients with LRD are intermediate-risk for TLS when renal dysfunction and/or renal involvement is present;
- Patients with IRD are high-risk for TLS when renal dysfunction and/or renal involvement is present OR when uric acid, phosphate and/or potassium levels are > ULN.

Legend. CLL= Chronic Lymphoid Leukaemia, CML= Chronic Myeloid Leukaemia, AML= Acute Myeloid Leukaemia, ALL= Acute Lymphoblastic Leukaemia, WBC= White Blood Count, LDH=Lactate Dehydrogenase, ULN= Upper Limit of Normal, LRD= Low Risk Disease, IRD= Intermediate Risk Disease, HRD= High Risk Disease.

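### Does the LTLS coding rule in section 9.3.4 conflict with the limits in Appendix I?

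*Combined protocol and SAP*

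**What the plan says.** **Section 9.3.4 (Clinical endpoints)** defines a 1/0 variable for LTLS from Day 3 to Day 8. It is present with two or more abnormalities, each being "a 25% increase or levels above normal for serum uric acid, potassium, and phosphate or a 25% decrease or levels below normal for calcium". Clinical TLS (CTLS) is LTLS plus at least one complication, and the renal one is called simply renal insufficiency. Rates are compared by dose and age group with a chi-square test.

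**Appendix I (13.1)** opens by saying that LTLS is diagnosed when two or more values "are more than or less than normal at presentation or if they change by at least 25% from baseline". A table follows at once:

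| Analyte | Limit | Change from baseline |
|---|---|---|
| Uric acid | at least 476 μmol/L (8 mg/dL) | 25% increase |
| Potassium | at least 6.0 mmol/L | 25% increase |
| Phosphorus | at least 1.45 (adults) or 2.1 (children) mmol/L | 25% increase |
| Calcium | at most 1.75 mmol/L | 25% decrease |

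A note adds: "For adolescents and adults, the values of phosphorus will be considered the same for the diagnosis of LTLS". For CTLS the appendix lists "increased creatinine level ≥ 1.5 ULN, cardiac arrhythmia/sudden death or seizure".

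**Appendix III (13.3)** moves intermediate-risk disease to high TLS risk when there is renal dysfunction or involvement, "OR when uric acid, phosphate and/or potassium levels are > ULN". Section 8.3.1 admits patients "at intermediate or high risk of TLS". Exclusion criterion 8 removes those who already have LTLS or CTLS at Visit 1.

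**The concern.** Read alone, section 9.3.4 is an operative rule that differs from Appendix I in three ways. It has no limits, it omits the one age-specific threshold although the comparison is between age groups, and it does not say what the 25% is measured from. Elsewhere the protocol does use *normal* for laboratory ranges: section 8.6.3.3 has sites send theirs to the sponsor, and section 8.7.4 uses the term for adverse event reporting.

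On that reading there is a concrete consequence. A patient could enter as high risk with, say, phosphate and potassium above the laboratory's upper limit but below the table limits. The table says no LTLS at Visit 1, so the patient is eligible. The same unchanged values on Day 3 would then be coded as an on-study event. CTLS requires LTLS, so it would inherit the error, and its undefined renal term adds a second loose end. At stake are the LTLS and CTLS rates reported by cohort, and how they compare across ages.

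**Working it through.** No sample size or power figure depends on this point. The main check is textual; the arithmetic only bounds what the wrong reading could do.

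**1. Where each missing element is found.**

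| Missing from the 9.3.4 rule | Supplied by |
|---|---|
| Numeric limits | Appendix I table. Sections 7.2 (objective), 8.6.3.3 (laboratory panel) and 8.6.4 (assessment) all refer LTLS to Appendix I |
| Phosphorus value by age | Appendix I table and the note under it |
| Baseline for the 25% change | Appendix I (change from baseline); sections 8.1 and 8.6.4 set baseline at Visit 1, Day 1 |
| Renal component of CTLS | Appendix I and the background in section 6.1: creatinine at least 1.5 times ULN |
| Data source | Section 8.6.4 and the endpoint definition in 8.8.2 both name local laboratory results |

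**2. Which meaning of *normal* fits.** The 9.3.4 sentence carries the same elements as the Appendix I lead sentence: two or more of the same four analytes, outside normal or changed by 25%. In the appendix those words introduce the table. Where the appendices mean a laboratory limit they write ULN, as in the creatinine criterion and the risk classification. The laboratory-range reading also breaks the eligibility rules. Applied at Visit 1, it would let a patient with two analytes above ULN in as high risk under Appendix III and shut the same patient out under exclusion criterion 8. The table reading has no such clash.

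**3. The two readings can differ.** Take an assumed patient, Visit 1 to on-study: uric acid 320 to 300 μmol/L, potassium 4.9 to 5.6, phosphorus 1.4 to 1.6, calcium 2.2 to 2.0 mmol/L.
- Ratios: 300/320 = 0.94; 5.6/4.9 = 1.14; 1.6/1.4 = 1.14; 2.0/2.2 = 0.91. None is a 25% change.
- Appendix I table: 0 abnormalities for a child; 1 for an adolescent or adult (1.6 is at least 1.45). No LTLS at any age.
- Laboratory range, assuming a potassium upper limit of 5.5 and a calcium lower limit of 2.1: potassium and calcium both count, so LTLS is coded present.

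The values and laboratory limits are assumptions. The example shows that the reading matters for some patients, not how often.

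**4. Size if the wrong reading were used.** Planned cohort size is about 24 (section 9.1). The adult pivotal rate on febuxostat is 8.1% (Appendix II, 120 mg SmPC, section 5.1).
- One recoded patient: 1/24 = 4.2 percentage points.
- Expected events per cohort: 24 × 0.081 = 1.94. With an assumed rate of 5% to 15%: 24 × 0.05 = 1.2 to 24 × 0.15 = 3.6.
- Five-group chi-square, 4 degrees of freedom, no continuity correction, 2/24 in four groups and the fifth as shown:

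| Fifth group | p |
|---|---|
| 3/24 | 0.98 |
| 4/24 | 0.83 |
| 7/24 | 0.107 |
| 8/24 | 0.034 |

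Six recoded patients in a single cohort (2 to 8), with none elsewhere, would be needed to cross 0.05.

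**The case for a change.** The strongest opposing case is that an endpoint rule should not have to be inferred. Section 9.3.4 is not silent but states a rule. Amendment 1 revised both that sentence and Appendix I, to allow plasma as well as serum, and left the wording unaligned. Nothing says outright whether the analysed variable is the investigator's eCRF assessment or one derived from the laboratory values. Clearer text would cost only a sentence.

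The omissions stand, and so does the point about the analysed variable. Neither leads to a different result under the plan as a whole. Section 8.6.4 has investigators apply Appendix I to local laboratory tests over the same Day 3 to Day 8 window and record the outcome in the eCRF, and 9.3.4 reads naturally as the 1/0 coding of that assessment. A derived variable would use the same local results and, by the references above, the same table. Section 9.5 leaves endpoint detail to a SAP finalised before database lock. The file contains no separate SAP text, so its wording cannot be checked either way.

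Two further arguments do not carry weight. Amendment 2 gives clearance and eGFR cut-offs for renal insufficiency, but in exclusion and withdrawal rules on severe insufficiency, submitted in Hungary; it does not define an endpoint. The age-specific phosphorus value can flip one analyte: a child at 1.9 mmol/L is negative on the table but positive where the local ULN is lower. LTLS needs two abnormalities, so that alone does not change the code.

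**Conclusion.** No change is required. Section 9.3.4 is a shortened paraphrase of Appendix I that lacks a cross-reference; it is not a competing definition. The limits, the phosphorus split, the baseline and the creatinine criterion can all be recovered from the protocol, and the laboratory-range reading would make its own eligibility rules inconsistent.

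This rests on the analyst reading 9.3.4 together with sections 7.2, 8.1 and 8.6.4 and Appendix I. If someone did use laboratory ranges, neither the number of patients recoded nor the direction by age group can be computed from the documents. Each such patient would move a cohort's rate by 4.2 points against about 1.9 expected events (1.2 to 3.6 under the assumed range), so reported rates would be disturbed more than the test. The endpoint is secondary, and the primary pharmacokinetic comparison is unaffected.

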
Sample size
	
A sample size of approximately 24 patients will be included in the Pharmacokinetic population for each age and dose group (pediatric cohorts 1-4 and adults).
 

 
Assuming a 10% screening failure rate, around 135 patients should be screened in order to enroll approximately a total

to Day 8 (AUC sUA₁₋₈). Comparisons will be made between febuxostat doses among the age groups and carried out on ITT and PK population.

- PK/PD: observed exposure-response data will be descriptively and graphically summarized by age and dose group. [REDACTED]

[REDACTED]

The aim of this analysis is to support the assumption of a comparable PK/PD relationship between pediatric patients ($\geq 6 < 18$ years of age) and adults and to evaluate if potential deviations in PK are clinically relevant. This analysis will be conducted on PK population.

[figure not shown]
- Clinical: incidence of LTLS and CTLS will be summarized through descriptive statistics by febuxostat dose and age group and their statistical comparison will be performed using a Chi Square test. Clinical endpoint analyses will be run on ITT population and for exploratory reasons on PP-population.
- Safety:
 - adverse events will be coded using the MedDRA dictionary. The incidence, severity, seriousness and causality of each TESS will be summarized by system organ class, preferred term by febuxostat dose and age group;
 - reasons for early termination will be summarized by febuxostat dose and age group;
 - laboratory findings and changes in PS will be reported by febuxostat dose and age group.All safety analyses will be run on the safety population.
- Assessment of the age-appropriate formulation

	
acceptability will be evaluated through a patient diary and summarized by means of descriptive statistics by febuxostat dose in children. The analysis will be conducted on the safety population.

--	---

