in adults. In fact, age is an independent risk factor for TLS development [9] and Acute Lymphoblastic Leukemia (ALL), the most common pediatric hematologic malignancy, has a particularly high proliferation rate and high sensitiveness to chemotherapy, thus predisposing children to a possible massive TLS with even fatal outcomes. Treatment possibilities for the management of TLS in pediatric patients miss an age-appropriate oral formulation of allopurinol. Therefore, children can receive a fully correct (weight-adjusted) TLS prophylaxis only with an intravenous treatment with rasburicase. Hence, considering the high cost and the limited access to rasburicase in some of the EU 28 countries, an age-appropriate febuxostat formulation certainly deserves clinical evaluation and may represent a valid alternative to the present therapy.

TLS usually develops in patients with aggressive Non-Hodgkin Lymphoma (NHL), Acute Lymphoblastic Leukemia (ALL), or Acute Myelogenous Leukemia (AML) [10]. In the pediatric population, TLS is more frequent in B-cell ALL or in Burkitt's lymphoma with high tumor burden [11-13]. An overall TLS incidence of 4.4% was reported in two multicentre studies of 1791 children and adolescents with NHL [11] and, of these, TLS occurred in 8.4% of patients with Burkitt's lymphoma or B-cell ALL.

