8. INVESTIGATIONAL PLAN

8.1 OVERALL STUDY DESIGN AND PLAN DESCRIPTION

This trial is designed as an open label, multi-centre, parallel group study to be conducted in approximately 40 sites. A total of 120 patients are expected to be treated in this trial distributed in 3 age-cohorts: 48 children (aged 6 to less than 12 years), 48 adolescents (aged 12 to less than 18 years) [1] and 24 adults, suffering from hematological malignancies at intermediate to high risk of TLS, with no access to rasburicase, and scheduled to receive the first cycle of cytotoxic chemotherapy regardless of line of treatment. The evaluation of TLS risk will be based on the classification model issued by Cairo and co-workers and published in the British Journal of Haematology [4], as reported in Appendix III: TLS Risk Assessment.

Potential hematologic patients at intermediate to high risk of TLS will be assessed for eligibility at the Screening Visit, which should be held up to 1 week (+2 days of accepted timeframe window) prior to the Start of Treatment (Day -9 to Day 1). The Start of Treatment (Visit 1, Day 1) will be scheduled 2 days prior to the planned start of first chemotherapy cycle; Screening Visit and Visit 1 (Day 1) may coincide.

After confirmation that all inclusion and none of the exclusion criteria are met, eligible patients will receive oral administration of the following dose of febuxostat per age group:

- Children

Cohort 1: 40 mg once daily;

Cohort 2: 60 mg once daily.

- Adolescents

Cohort 3: 80 mg once daily;

Cohort 4: 120 mg once daily.

- Adults

120 mg once daily.

The two dose levels per children and adolescent groups will be sequentially administered to cohort. The first ≈ 24 children will receive the lower dose of 40 mg once daily and the first ≈ 24 adolescents the dose of 80 mg once daily. Afterwards, the higher doses will be administered: 60 mg once daily to children, and 120 mg once daily to adolescents. Cohort 1, Cohort 3 and adults treatments will start simultaneously. The control group of adult patients has been chosen to allow the comparison of PK/PD parameters between the pediatric ($\geq 6 < 18$ years) and the adult populations.

The final total number of patients/patients distributed in each age/dose cohort might slightly deviate

from the planned number since patients who satisfactory passed the screening have the right to be treated.

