The pharmacokinetic of febuxostat has been extensively investigated both in adult healthy subjects and in patients with hyperuricemia and gout. In general, febuxostat PK parameters estimated by population PK analyses in patients are consistent with those obtained from healthy subjects, indicating that healthy subjects are representative for PK assessment in the patient population with gout. Pharmacokinetic analyses in special populations demonstrated that dosage adjustment is not required in patients with mild or moderate renal impairment [29]. The investigation on the influence of covariates such as age, weight and gender on febuxostat PK, PD and safety were considered not clinically meaningful, suggesting no need of dose adjustment based on these parameters in adult patients [22]. These data were taken into account to optimize the sample size of the present study, as per guideline CHMP/EWP/147013/2004 [33]. According to the PK profile of febuxostat, the pharmacokinetics in adolescent patients is expected to be similar to the one in adults, whilst minor differences in the pharmacokinetics of children aged 6 to 11 years are expected.

To resemble the FLORENCE study outline [30] and the future clinical practice, patients with hematological malignancies who are scheduled to be treated with cytotoxic chemotherapy, regardless of the line of treatment, and at intermediate to high risk of TLS, will be screened. Eligible patients will receive treatment for 7 to 9 consecutive days, starting from 2 days prior to chemotherapy. Children and adolescents will be administered one out of the two dose levels of febuxostat, 40 or 60 mg for children, and 80 or 120 mg for adolescents. As for an extreme cautious approach, the two dose levels in children and adolescents will be sequentially administered (Cohort 2 after Cohort 1 and Cohort 4 after Cohort 3). The first ≈ 24 children will receive the lower dose of 40 mg once daily, and the first ≈ 24 adolescents the dose of 80 mg once daily. Afterwards, the higher doses will be administered: 60 mg once daily to children and 120 mg once daily to adolescents. Adults will receive 120 mg once daily in accordance to the treatment schedule previously adopted in the FLORENCE study [30]. No restriction will be applied to the enrolment of patients with different types of hematological malignancies, nor to the chemotherapy regimen with the exception of those including investigational products. The inclusion of

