8.5 TREATMENTS

8.5.1 Treatment Allocation

The study will be performed according to an open design; no blinding technique will be adopted.

Eligible patients will receive study treatment at Visit 1 (Day 1) after completing the relevant “prior to drug administration” procedures and re-checking of the eligibility criteria.

The IMP box assignment will be performed by means of the IxRS system (see section 10.1.2) without any randomized allocation. The first ≈24 children will be allocated to the 40 mg dose, the following ≈24 children to the 60 mg dose. The first ≈24 adolescents will be allocated to the 80 mg dose, the following ≈24 adolescents to the 120 mg dose. The ≈24 adults will be allocated to the 120 mg dose.

For children, the 20 mg febuxostat tablets will be used, whereas for adolescents and adults the market product ADENURIC® 80 mg and 120 mg will be employed as represented below:

Table 1. Febuxostat: Treatment dose and form

Patient Population	Treatment dose	Treatment form
Children	febuxostat 40 mg	2 tablets 20 mg
	febuxostat 60 mg	3 tablets 20 mg
Adolescents	ADENURIC® 80 mg	1 tablet 80 mg

	ADENURIC® 120 mg	1 tablet 120 mg
Adults	ADENURIC® 120 mg	1 tablet 120 mg

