1: PRESENCE presence of LTLS in addition to 1 or more of the following significant clinical complications: renal insufficiency, cardiac arrhythmias, sudden death and seizures.

0: ABSENCE absence of LTLS or absence of any significant clinical complications: renal insufficiency, cardiac arrhythmias, sudden death and seizures.

Chi Square test will be used to compare statistically the rate incidence of LTLS and CTLS by dose and age group.

The efficacy analyses will be run on the ITT population and for exploratory reasons on PP-population.

- ***Assessment of the age-appropriate formulation acceptability***

Assessment of the age-appropriate formulation acceptability will be evaluated through a 5-point

hedonic scale anchored with the word super bad and super good and summarized by means of descriptive statistics by febuxostat dose in children. The analysis will be conducted on the safety population.

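### LTLS and CTLS are compared across non-randomised dose and age groups without using the TLS risk class assessed at entry, so an unequal risk mix can appear as an age or dose difference

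*Combined protocol and SAP*

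**What the plan says.** Section 9.3.4 (clinical endpoints) states: "Chi Square test will be used to compare statistically the rate incidence of LTLS and CTLS by dose and age group". The synopsis agrees: "their statistical comparison will be performed using a Chi Square test". Neither place gives a stratum, covariate or standardisation. Section 9.3.5 names no subgroup factor. Section 9.5 defers detail to a SAP that is not among the documents supplied.

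On how the groups arise, section 8.5.1 says: "The IMP box assignment will be performed by means of the IxRS system (see section 10.1.2) without any randomized allocation". Children and adolescents fill the lower-dose cohort first and the higher-dose cohort afterwards. Section 8.2 adds: "No restriction will be applied to the enrolment of patients with different types of hematological malignancies".

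On TLS risk, section 8.3.1 requires patients to be "at intermediate or high risk of TLS [4], and". Section 8.1 says: "The evaluation of TLS risk will be based on the classification model", and Appendix III gives the decision trees and the rules for moving between classes, for example: "Patients with IRD are high-risk for TLS when renal dysfunction and/or renal involvement is present". Section 8.6.3.1 has sites record tumour type and renal dysfunction or involvement. The assigned risk class is not listed there, nor in the flow chart.

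The study rationale (section 6.1) states that "age is an independent risk factor for TLS development" and that acute lymphoblastic leukaemia, the most common paediatric haematological malignancy, predisposes children to massive TLS.

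**The concern.** The protocol gives its own reasons to expect TLS risk to differ by age, does not restrict malignancy type, and then compares TLS incidence across age groups with a test that ignores risk. If the children include more high-risk patients than the adults, their crude LTLS incidence will be higher even if age and dose make no difference. A favourable mix could equally hide a real difference. The same applies, less strongly, to 40 mg against 60 mg in children and 80 mg against 120 mg in adolescents. Entry criteria are the same for these cohorts, but they enrol one after the other and nothing balances them on risk.

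Section 9.3.4 labels these efficacy analyses, and section 6.3 says the study may help to identify the best paediatric dose. A crude paediatric excess of LTLS could therefore be read as weaker control in that group. Without a table by risk class, a reader of the report could not judge whether case mix explains it.

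**Working it through.** **The plan's own figure.** The sample size reproduces: 5 groups × 24 = 120, and 120 / (1 − 0.10) = 133.3, against about 135 stated in section 9.1. No visible text gives a significance level, power or sample size for the LTLS/CTLS test, so that test has no figure to reproduce.

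**Expected events.** The 120 mg SmPC in Appendix II (section 5.1) reports, for adults on febuxostat in the pivotal study, LTLS 8.1% and CTLS 1.7%. If these rates applied here:
- LTLS: 24 × 0.081 = 1.9 per group; 120 × 0.081 = 9.7 overall.
- CTLS: 24 × 0.017 = 0.4 per group; 120 × 0.017 = 2.0 overall.

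**Size of the case-mix effect.** Assumptions, none of them in the documents: 8.1% applies at a 50:50 mix of risk classes; high-risk patients are k times as likely to have LTLS; age and dose have no effect.
- Intermediate rate = 0.081 / (0.5 + 0.5k); high rate = k × intermediate rate.
- Group rate = (1 − h) × intermediate + h × high, where h is the high-risk share.

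With h = 0.8 in a paediatric group and 0.4 in adults:

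| k | Intermediate | High | Paediatric | Adult | Crude ratio | Extra LTLS patients per 24 |
|---|---|---|---|---|---|---|
| 2 | 5.40% | 10.80% | 9.72% | 7.56% | 1.29 | 0.5 |
| 3 | 4.05% | 12.15% | 10.53% | 7.29% | 1.44 | 0.8 |
| 4 | 3.24% | 12.96% | 11.02% | 7.13% | 1.55 | 0.9 |

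For other mixes with k from 2 to 4, 60% against 40% gives 1.14 to 1.27, and 90% against 30% gives 1.46 to 1.95. Equal mixes give 1.00. Within each class the ratio is 1.00 throughout, so stratifying removes this particular bias.

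**A rough guide to the gradient.** Section 6.1 quotes TLS in 4.4% of children and adolescents with non-Hodgkin lymphoma, and in 8.4% of those with Burkitt's lymphoma or B-cell ALL: 8.4 / 4.4 = 1.9. This contrasts disease types rather than Appendix III classes, but shows that case mix alone can move incidence about two-fold.

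**Effect on the test.** Assuming two-sided 0.05 and 24 against 24, simulation gives a rejection rate of about 4% for equal mixes. At 80% against 40% it is 4.8% to 6.6% for k from 2 to 4. Over a wider range (30% against 70% and 20% against 80%, k up to 6) it is 4.5% to 12%. The shift is small because the test has little power: 13% for 8.1% against 16.2%, where 80% power would need 255 per group.

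**What stratifying buys.** Take k = 4, with 19 of 24 paediatric patients and 10 of 24 adults high risk. The crude difference is biased by (19 − 10)/24 × (12.96% − 3.24%) = 3.6 percentage points. A Mantel-Haenszel risk difference removes that bias, but root-mean-square error stays at about 9.0 points either way. The 10 high-risk adults have no LTLS event in (1 − 0.1296)^10 = 25% of trials.

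**The case against.** The strongest reply is that this matters little and that stratifying delivers little. LTLS and CTLS are secondary, and section 7.2 sets out only to evaluate their occurrence, whereas it sets out to compare pharmacodynamics. Bridging from adults rests on PK and PK/PD (section 6.1), and no visible dose decision depends on this test. The illustrative bias is 0.5 to 0.9 patients per 24, while the exact 95% interval for 2/24 runs from 1.0% to 27.0%. All of this stands. It limits the weight of the point, but does not justify reporting crude comparisons alone when a risk classification is already required for entry.

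Four stronger readings are tempting, and the documents do not support them.

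- A reader might infer that stratification would show whether febuxostat protects one age group less. It would not. Section 6.1 calls age an independent risk factor, there is no arm without febuxostat, and Appendix I sets the LTLS phosphate threshold at 2.1 mmol/L for children but 1.45 mmol/L for adolescents and adults.
- A reader might call the risk class the strongest known predictor of TLS. No section says so. It is the protocol's own risk classification.
- A reader might pool the 96 paediatric patients against the 24 adults to gain precision. That merges four dose cohorts and mixes the two phosphate thresholds.
- A reader might want the stratified estimate for CTLS as well. About 2 events in 120 cannot support one.

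Parts of the statistical text are blacked out, and neither a separate SAP nor the eCRF is available. The finding is therefore that the visible plan specifies no adjustment. The eCRF may already hold the risk class.

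**Conclusion.** The point holds as a modest, inexpensive improvement. The visible plan compares LTLS and CTLS without adjustment across groups that differ by design in age and order of entry, and leaves unused a risk classification required for eligibility. A crude LTLS ratio of about 1.3 to 1.5 could arise with no age or dose effect if LTLS is 8.1% at a 50:50 mix, the gradient is 2 to 4 fold and the high-risk shares are 80% and 40%. It would be nearer 1 with more similar mixes and up to about 1.9 with 90% against 30%. The true mix and gradient are unknown. With about 2 LTLS events per group, a spurious significant result is unlikely; the risk is a misread incidence table. Stratifying reduces case-mix bias. It does not isolate a drug effect by age, and it does not make the comparison precise.

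**What to change.** In section 9.3.4 and the SAP, before database lock:

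1. Tabulate the Appendix III risk class (intermediate, high) by dose and age group.
2. Report LTLS as n/N with exact 95% intervals by risk class within each group.
3. Base any LTLS comparison of a paediatric cohort with adults, or of the two sequential dose cohorts within an age group, on a risk-stratified estimate (for example a Mantel-Haenszel risk difference) with an exact stratified test. Keep the crude comparison as supportive.
4. Keep CTLS descriptive, and do not rely on a pooled comparison of 96 paediatric patients with 24 adults.
5. State that stratification leaves in place any independent age effect, the age-specific phosphate threshold and differences in chemotherapy.
6. Confirm that the eCRF records the assigned risk class, and add the field if it does not.

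The cost is SAP wording, one table and at most one eCRF field for a classification that sites already make. The downside is sparse strata: one event in 12 patients has an exact 95% interval of 0.2% to 38.5%. The stratified results should be read as a check on case mix, not as evidence of similarity.
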